The treatment duration or follow-up time on digoxin (or statins) alone will begin accumulating on the first day of digoxin (or statins) prescription and continue with the subsequent continuous digoxin (or statins) prescriptions until: 1) a prescription for dronedarone (or amiodarone) overlapping the digoxin (or statins) days supplied, or 2) the end of the digoxin (or statins) days supplied (in addition to a grace period of up to 30 days, to account for non-adherence), 3) the occurrence of the outcome, 4) the enrollment end of membership, 5) the end of the observation period, whichever comes first. The follow-up time of the concomitant use of digoxin (or statins) and dronedarone (or amiodarone) will be defined using the same methodology as described above. It will however begin on the first day of overlapping days supplied for digoxin (or statins) and dronedarone (or amiodarone) and will finish with the end of overlap of the days supplied for digoxin (or statins) and dronedarone (or amiodarone) (in addition to a grace period of up to 30 days) or the other endpoints, whichever comes first. Prescriptions will be treated as continuous if they are not interrupted by a break of greater than 30 days. If a gap of greater than 30 days occurred, patients may still contribute follow-up time (defined as a separate treatment episode) to digoxin (or statins) alone or the concomitant medications as appropriate, until they are right-censored at the first occurrence of: 1) the outcome, 2) the enrollment end of membership, and 3) the end of the observation period.

Given that digoxin (or statins) may be administered at a lower dose when used in combination with dronedarone than the use of digoxin (or statins) alone, and the drug interaction effect may be dose-related, the average daily dose of digoxin (or statins) will be adjusted for as a covariate in the analysis. It will be calculated as the total quantity prescribed divided by the total days supplied. If a statistically significant association of interaction is observed, further analysis will be performed to check dose-response relationship. For statins, the analyses will be conducted at equally effective doses which will address the effect of dose with the same cholesterol lowering effect. Based on published literature comparing statins efficacy, the following equally effective doses will be used in the secondary analysis for statins: atorvastatin 10mg, simvastatin 20mg, lovastatin 40mg, and pravastatin 40mg¹⁻².

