3.5 COVARIATE(S)

The following covariates will be adjusted for in the multivariate analyses: age at baseline, gender, cohort entry date, duration of AF/AFL, congestive heart failure (CHF) history, diabetes history, hypertension history, stroke history, myocardial infarction history, and dose of digoxin (or statins). The major medications that are known to have potent interactions with statins or digoxin will additionally be adjusted for as potential confounders. For digitalis intoxication, the medications will be those with potent interactions, including arbutamine, atazanavir, calcium chloride, calcium gluceptate, calcium gluconate, and saquinavir. The drugs with interaction that are generally considered to be moderate (e.g. aspirin) or mild (e.g. acetaminophen) will not be considered⁷. For the outcome of rhabdomyolysis and myopathy, the major medications will include erythromycin, clarithromycin, azithromycin, fusidic acid, warfarin, dicoumarol, nefazodone, ketoconazole, itraconazole, cholestyramine, mibefradil, digoxin, gemfibrozil, cyclosporine, chlorzoxazone, and vitamins niacin⁸. History of renal failure (except for acute renal failure) will also be adjusted for the outcome of rhabdomyolysis and myopathy.

The history of the medical conditions will be defined as a diagnosis in the baseline period based on the ICD-9 codes (codes to be provided). The count of the number of diagnoses of AF/AFL in the baseline period will be used as a surrogate for the duration of AF/AFL since the accurate information is not available in the LabRx database. All medications will be identified using the National Drug Code (NDC) directory. Maintained by the Food and Drug Administration (FDA), NDC is a code-set that serves as a universal product identifier for human drugs and biologics. The directory consists of prescription and a few selected over-the-counter drugs that are in commercial distribution in the United States. The products have been listed in accordance with the Drug

Listing Act and applicable Code of Federal Regulations for submitting drug product information to the FDA (see: <http://www.fda.gov/cder/ndc/>).

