3.7 STATISTICAL ANALYSIS

Descriptive statistical analysis will be performed to characterize the study participants. Cox proportional hazards regression modeling will be used to provide estimates of the relative hazard of the outcome of interest associated with concomitant use of digoxin (statins) and dronedarone, and concomitant use of digoxin (statins) and amiodarone, using digoxin (statins) alone as the reference group. If a statistically significant association of interaction is observed, further analysis will be done to estimate dose-response relationship with cumulative dose and treatment duration.

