7 TABLES AND FIGURES

Table 1 Distribution of gender, age, and region of patients in the LabRx as of 2008 and in the US general population in 2005

Attributes	LabRx	US Population (2005)*
Male	50%	49%
US Region	Total Lives (%)	Total Lives (%)
Northeast	22%	19%
North Central	30%	22%
South	30%	36%
West	18%	23%
Age Group	Total Lives (%)	Total Lives (%)
00-20	28%	27%
21-39	32%	29%
40-64	34%	32%
65+	6%	12%

*Statistical abstract, US Census

Table 2 Age distribution in AF/AFL Patients in the LabRx (1/1985-3/2008)

Age (yrs)	N	%
18-29	3,705	1.5
30-49	36,089	14.2
50-64	86,431	34.1
>65	127,516	50.3
Total	253,741	100.0

Table 3 Estimated sample size

Outcome	Incidence in literature	Size of cohort*		Hazard Ratio
Digitalis intoxication	1.1% ⁹	3 years	25,000	1.59
		4 years	32,000	1.51
		5 years	44,000	1.42
Rhabdomyolysis /myopathy	0.3% ¹⁰⁻¹¹	3 years	58,000	1.77
		4 years	70,000	1.69
		5 years	86,000	1.61

Given alpha=0.05 (two-sided), statistical power = 80%, prevalence of dronedarone in the cohort = 17.1%, baseline event rate = 1.1% for digitalis intoxication, and 0.3% for rhabdomyolysis /myopathy, and right censoring rate = 30%

*Estimated based on the preliminary results of the available LabRx data as of August 31, 2010

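### The digitalis-intoxication model adjusts for heart failure only as a yes/no baseline diagnosis, so residual confounding by heart-failure severity is possible, in a direction and size the protocol does not give

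*Protocol*

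**What the plan says.** Section 3.5 (Covariates) adjusts for "congestive heart failure (CHF) history, diabetes history, hypertension history, stroke history, myocardial infarction history", among other terms, and defines them together: "The history of the medical conditions will be defined as a diagnosis in the baseline period based on the ICD-9 codes". Only the list of codes is left open; the form of the variable, a diagnosis present or absent at baseline, is fixed.

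The same section treats atrial fibrillation or flutter differently: "The count of the number of diagnoses of AF/AFL in the baseline period will be used as a surrogate" for its duration. That is the only condition with a graded measure. History of renal failure is added for rhabdomyolysis and myopathy, but not for digitalis intoxication.

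Section 3.3 adds that "the average daily dose of digoxin (or statins) will be adjusted for as a covariate in the analysis". Section 3.7 compares dronedarone co-use and amiodarone co-use with digoxin alone in a Cox model, "using digoxin (statins) alone as the reference group".

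**The concern.** The protocol accepts CHF as a confounder of the digoxin comparison. If risk of intoxication rises with severity, and severity among CHF patients differs between digoxin-alone and co-use time, a present/absent term removes only part of the confounding. Both conditions are assumptions; neither is stated in the protocol.

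The other terms in the digoxin model offer little direct help. The listed interacting drugs (arbutamine, atazanavir, calcium salts, saquinavir) do not grade heart failure, and renal history is absent from this model. Average digoxin dose and the other comorbidities could absorb some of a severity difference, but only indirectly.

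Two features of the plan make a modest bias worth attention. Section 5 allows the final analysis of an outcome to start at 336 events, a number sized for a hazard ratio of 1.5, so there is little slack. And the dose-response work in Sections 3.3 and 3.7 is done only if the association is statistically significant, so a downward bias could remove both the signal and the analysis meant to examine it. An upward bias would exaggerate the interaction.

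**Working it through.** **1. The plan's own figure.** Inputs from the Table 3 footnote: "Given alpha=0.05 (two-sided), statistical power = 80%, prevalence of dronedarone in the cohort = 17.1" per cent. Schoenfeld's formula gives the events needed for a hazard ratio of 1.5:

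(1.960 + 0.842)² / [0.171 × 0.829 × (ln 1.5)²] = 7.849 / (0.14176 × 0.16440) = 336.8.

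This agrees with the 336 events in Section 5. The point does not rest on a sample-size error.

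**2. The significance threshold at 336 events.** √(336 × 0.14176) = 6.90, so the smallest observed hazard ratio that reaches two-sided 0.05 is exp(1.960 / 6.90) = 1.33. Power for an expected observed ratio H is Φ(6.90 × ln H − 1.960); for H = 1.5 it is 80%.

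**3. Residual bias after yes/no CHF adjustment.** All inputs here are assumptions, because the protocol gives no CHF share, no severity split and no severity effect. Let c be the CHF share (equal in both groups), s0 and s1 the severe share among CHF patients on digoxin alone and on co-use, and R the severity hazard ratio. Non-severe CHF is taken to carry the same hazard as no CHF.

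- Factor within CHF patients: f = [1 + s1(R − 1)] / [1 + s0(R − 1)]
- Approximate share of events from CHF patients: w = c[1 + s0(R − 1)] / {c[1 + s0(R − 1)] + 1 − c}
- Residual factor in the adjusted model: b = f^w

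For c = 0.40, s0 = 0.30, s1 = 0.10:

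- R = 2: f = 1.10/1.30 = 0.846; w = 0.52/1.12 = 0.464; b = 0.925; a true 1.5 reads 1.39.
- R = 3: f = 1.20/1.60 = 0.750; w = 0.64/1.24 = 0.516; b = 0.862; a true 1.5 reads 1.29.

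Reversed, s0 = 0.10, s1 = 0.30, R = 2: f = 1.30/1.10 = 1.182; w = 0.44/1.04 = 0.423; b = 1.073; a true 1.5 reads 1.61. With s0 = s1, f = 1 and there is no bias.

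**4. Range over the CHF share, with power at 336 events.**

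| CHF share | Severe, alone v co-use | R | b | True 1.5 reads | Power |
|---|---|---|---|---|---|
| any | equal | any | 1.00 | 1.50 | 80% |
| 20% | 30% v 10% | 2 | 0.960 | 1.44 | 71% |
| 20% | 30% v 10% | 3 | 0.921 | 1.38 | 61% |
| 40% | 30% v 10% | 2 | 0.925 | 1.39 | 62% |
| 40% | 30% v 10% | 3 | 0.862 | 1.29 | 43% |
| 60% | 30% v 10% | 2 | 0.895 | 1.34 | 53% |
| 60% | 30% v 10% | 3 | 0.816 | 1.22 | 29% |
| 40% | 10% v 30% | 2 | 1.073 | 1.61 | 91% |

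A threefold difference in the severe share is a fairly strong imbalance. With 20% v 10%, c = 0.40 and R = 2, b is 0.962 and a true 1.5 reads 1.44.

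**5. Whether the data for a better variable exist.** Section 3.4 already uses hospitalisation claims to define outcomes. Section 3.2 excludes patients with less than six months of enrolment at cohort entry, so every patient has a six-month look-back. A heart-failure admission in that window can be derived without new data.

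**The case against.** The strongest objection is that no passage says heart-failure severity differs between the exposure groups, or which group is sicker. That stands. A reader might infer that dronedarone goes to patients with milder heart failure, so that the present/absent term leaves a difference that hides an interaction. The protocol does not say how dronedarone is allocated by severity, and the reverse imbalance would inflate the hazard ratio.

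A reader might also reach a larger bias from overall shares. With a recent heart-failure admission in 10% of co-use time and 25% of digoxin-alone time, and a relative risk of 2, the factor is 1.10/1.25 = 0.88. That calculation treats CHF as absent from the model. If CHF prevalence were 20% on co-use and 50% on digoxin alone, with half of the CHF patients admitted in each group, the overall shares would be exactly 10% and 25%, yet the factor within CHF patients would be 1.5/1.5 = 1.00. Overall shares cannot measure what remains after CHF adjustment; only a calculation within CHF patients can.

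It can also be said that the number of levels of a covariate is usually settled in the analysis plan, that a binary comorbidity code is common in claims studies, and that dose, age and other comorbidities absorb part of any difference. The last is fair and makes the illustrated factors upper-end figures for their inputs. The first has less force, because Section 3.5 does not leave the form open: it fixes a diagnosis in the baseline period and defers only the codes.

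**Conclusion.** The point holds as a limitation with a cheap remedy, not as a demonstrated bias. In the digitalis-intoxication model CHF is a yes/no baseline diagnosis, so confounding by severity may remain; its existence, size and direction cannot be determined from the protocol. Under the central assumptions in the working (CHF in 40% of both groups, severe share 30% v 10%, severity hazard ratio 2 to 3) the residual factor is about 0.93 to 0.86. A true 1.5 then reads about 1.39 to 1.29, against a threshold of about 1.33 at 336 events. Reversing the imbalance gives about 1.07 at severity hazard ratio 2, and equal shares give none. The documents do not support the conclusion that an interaction will be hidden. This is a desirable improvement rather than a necessary correction.

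**What to change.** In Section 3.5, for the digoxin model:

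1. Replace CHF history by three levels, measured in the six months before cohort entry: no diagnosis; diagnosis without a heart-failure admission; heart-failure admission.
2. Add a sensitivity analysis that re-measures the variable in the six months before the start of each exposure episode. Exposure changes during follow-up, so status at cohort entry may be out of date when dronedarone is added. This belongs in a sensitivity analysis because the later window can include events that occurred on earlier study treatment.
3. Repeat the digoxin analysis in patients without a heart-failure admission in the window.

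Tabulating the three levels by exposure group would show whether an imbalance exists, and in which direction.

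The cost is some wording and one variable derived from hospital claims already in the database. A three-level factor uses two indicator terms instead of one, which is small against several hundred expected events. The restricted analysis will have fewer events and a wider interval; the protocol gives no figure from which to say how much wider.

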3.6 SAMPLE SIZE

We calculated sample size based on the likelihood ratio test in the context of a Cox proportional hazards regression analysis. The preliminary analysis of the last five-year data in the LabRx suggested that there might be about 44,000 participants for the cohort of digoxins and about 86,000 participants for the cohort of statins during the next 5-year cohort accrual period (07/2009-06/2014). With these figures, the study would be able to rule out a hazard ratio of 1.42 for the outcome of digitalis intoxication, and a hazard ratio of 1.61 for the outcome of rhabdomyolysis and myopathy with the assumptions of 0.05 alpha level (type I error), 80% statistical power (type II error), 17.1% prevalence of dronedarone use in the study population (the sponsor's prediction), 1.1% baseline incidence rate for the outcome of digitalis intoxication⁹, and 0.3% baseline incidence rate for the outcome of rhabdomyolysis and myopathy¹⁰⁻¹¹. For a 4-year cohort accrual period (07/2009-06/2013), we estimate that the study would be able to rule out a hazard ratio of 1.51 with over 32,000 participants for the outcome of digitalis intoxication, and a hazard ratio of 1.69 with over 70,000 participants for the outcome of rhabdomyolysis and myopathy with the same assumption. For a 3-year cohort accrual period (07/2009-06/2012), we estimate that the study would be able to rule out a hazard ratio of 1.59 with over 25,000 participants for the outcome of digitalis intoxication, and a hazard ratio of 1.77 with over 58,000 participants for the outcome of rhabdomyolysis and myopathy with the same assumption (see [Table 3](#)).

3.7 STATISTICAL ANALYSIS

Descriptive statistical analysis will be performed to characterize the study participants. Cox proportional hazards regression modeling will be used to provide estimates of the relative hazard of the outcome of interest associated with concomitant use of digoxin (statins) and dronedarone, and concomitant use of digoxin (statins) and amiodarone, using digoxin (statins) alone as the reference group. If a statistically significant association of interaction is observed, further analysis will be done to estimate dose-response relationship with cumulative dose and treatment duration.

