Rhabdomyolysis and myopathy will be defined by an algorithm based on the ICD-9 codes, lab testing, and/or hospitalization that have been validated in a published study.

Covariates: Covariates in the multivariate analyses will include age at baseline, gender, cohort entry date, duration of AF/AFL, congestive heart failure (CHF), diabetes, hypertension, stroke, myocardial infarction, and dose of digoxin (or statins). The major medications that are known to have potent interactions with digoxin or statins will additionally be adjusted as potential confounders, while for rhabdomyolysis and myopathy, chronic renal failure will also be adjusted for.

Statistical analysis: Descriptive statistical analysis will be conducted to characterize the study participants. Cox proportional hazards regression modeling will be used to provide estimates of the relative hazard of the outcome of interest associated with concomitant use of digoxin (statins) and dronedarone, concomitant use of digoxin (or statins) and amiodarone, using digoxin (statins) alone as the reference group. Dose-response relationship with cumulative dose and treatment duration will be estimated if a positive association is observed.

Timelines: The interim study reports will be submitted annually in December, 2010 to 2014. The final study report will be submitted in December 2016 at the latest. The study observation period will be from July 20, 2009 (the launch date of dronedarone in the US to the latest date of available data by August 31 of each year in the yearly study report).

TABLE OF CONTENTS

LIST OF TABLES	6
LIST OF FIGURES	6
ABBREVIATIONS	7
1 INTRODUCTION	8
2 STUDY OBJECTIVE(S)	8
3 METHODS	8
3.1 STUDY DESIGN	8
3.1.1 Source population(s)/database(s) used	9
3.2 STUDY POPULATION.....	9
3.3 EXPOSURE MEASUREMENT	9
3.4 OUTCOME(S) OF INTEREST	11
3.5 COVARIATE(S).....	11
3.6 SAMPLE SIZE.....	12
3.7 STATISTICAL ANALYSIS.....	12
4 CONFIDENTIALITY AND ETHICAL CONSIDERATIONS	12
5 STUDY TIMELINES	12
6 REFERENCES	13
7 TABLES AND FIGURES	14
8 APPENDICES	17

LIST OF TABLES

Table 1 Distribution of gender, age, and region of patients in the LabRx as of 2008 and in the US general population in 2005	14
Table 2 Age distribution in AF/AFL Patients in the LabRx (1/1985-3/2008).....	15
Table 3 Estimated sample size	16

LIST OF FIGURES

N/A

ABBREVIATIONS

AF	Atrial fibrillation
AFL	Atrial flutter
CHF	Congestive heart failure
CPT	Current Procedural Terminology
GCP	Good Clinical Practice

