2 STUDY OBJECTIVE(S)

The goal of this study is to provide safety information about dronedarone use in the US. The objectives of this study are to evaluate the possibility of dronedarone increasing the dose-related adverse events of the following concomitantly used drugs: digoxin (digitalis intoxication) and statins (rhabdomyolysis and myopathy).

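### Dose-response is estimated only if the pooled result passes an inconsistently worded trigger, and the named metrics are cumulative dose and duration, so a null pooled result could be reported with no exposure-by-dose estimate

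*Protocol*

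**What the plan says.** Section 2 sets the aim: "to evaluate the possibility of dronedarone increasing the dose-related adverse events of the following concomitantly used drugs". Section 3.3 gives the reason for handling dose, namely that "the drug interaction effect may be dose-related", and that digoxin or a statin may be given at a lower dose alongside dronedarone. It defines average daily dose as quantity prescribed over days supplied and states that "the average daily dose of digoxin (or statins) will be adjusted for as a covariate in the analysis".

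The trigger for a dose-response analysis appears in four places:

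- Section 3.7: "If a statistically significant association of interaction is observed, further analysis will be done to estimate dose-response relationship with cumulative dose and treatment duration".
- Section 3.3: "If a statistically significant association of interaction is observed, further analysis will be performed to check dose-response relationship". No metric is named.
- Synopsis, exposure paragraph: the same significance condition as Section 3.3, again without a metric.
- Synopsis, statistical analysis paragraph: "Dose-response relationship with cumulative dose and treatment duration will be estimated if a positive association is observed".

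Section 3.3 also plans a secondary statin analysis at equally effective doses. Its position directly after the conditional sentence leaves it unclear whether the condition applies to it. No exposure-by-dose analysis is clearly stated to run regardless of the pooled result.

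**The concern.** Three features do not fit the protocol's own rationale.

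1. **The trigger is stated in two ways.** A non-significant hazard ratio of 1.3 would start the dose analysis under the synopsis's statistical paragraph but not under Sections 3.3 and 3.7.
2. **The condition depends on a pooled estimate.** If the effect varies with dose, the pooled hazard ratio averages over dose levels and an effect at higher doses is diluted in it. Adjusting for daily dose as a main effect removes confounding by dose. It does not show whether the dronedarone hazard ratio differs between dose levels.
3. **The metric changes.** Section 3.3 reasons about dose level and builds a daily-dose variable. Section 3.7 then names cumulative dose and duration. Cumulative dose mixes dose with time on treatment: a long user at a low dose can have the same total as a short user at a high dose.

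At stake is a safety report that gives a non-significant pooled result with no estimate of the dronedarone effect at the higher doses of the co-administered drug.

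**Working it through.** **Inputs.** Section 3.6 gives "0.05 alpha level (type I error), 80% statistical power (type II error), 17.1% prevalence of dronedarone use in the study population", five-year cohorts of about 44,000 (digoxin) and 86,000 (statins), baseline rates of 1.1% and 0.3%, and design hazard ratios of 1.42 and 1.61. The note to Table 3 adds a two-sided alpha and 30% right censoring. Section 5 ties 336 events to a hazard ratio of 1.5.

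**The plan's own figure.** Schoenfeld's formula is D = (1.96 + 0.8416)² / [p(1−p)(ln HR)²], with p(1−p) = 0.171 × 0.829 = 0.1418. For HR 1.5, D = 7.849 / (0.1418 × 0.1644) = 336.8. The stated 336 is reproduced; power with 336 events is 79.9%. Without the censoring, the same formula gives detectable hazard ratios of 1.57/1.49/1.40 (digoxin; 3, 4 and 5 years) and 1.76/1.67/1.59 (statins), within about 0.02 of Table 3.

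**Events.** The protocol does not state them for five years. Cohort times rate gives 44,000 × 0.011 = 484 and 86,000 × 0.003 = 258. If the 30% censoring removes events in proportion, these become 484 × 0.7 = 339 and 258 × 0.7 = 181. Both ends are carried.

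**Probability that the significance condition skips the dose analysis** = 1 − Φ(ln HR × √(0.1418 D) − 1.96).

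Example: D = 484 and HR 1.3 give 0.2624 × 8.283 − 1.96 = 0.213, Φ = 0.584, skip 42%.

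| Events | HR 1.2 | HR 1.3 | HR 1.5 | Design HR |
|---|---|---|---|---|
| Digitalis, 484 | 67% | 42% | 8% | 17% (1.42) |
| Digitalis, 339 | 76% | 56% | 20% | 32% (1.42) |
| Rhabdomyolysis/myopathy, 258 | 80% | 65% | 31% | 18% (1.61) |
| Rhabdomyolysis/myopathy, 181 | 85% | 74% | 46% | 33% (1.61) |
| Section 5 trigger, 336 | 76% | 56% | 20% | – |

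If dronedarone exposure were 10% instead of 17.1% (an assumption), the 484-event figures would be 59% at HR 1.3 and 36% at 1.42.

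**How far apart the two triggers are.** Suppose a positive association means only an estimate above 1 (an assumption). The skip probability is then Φ(−ln HR × √(0.1418 D)). At HR 1.3 this is Φ(−2.17) = 1% and Φ(−1.82) = 3% for 484 and 339 digitalis events, and Φ(−1.59) = 6% and Φ(−1.33) = 9% for 258 and 181 rhabdomyolysis/myopathy events.

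**Direction under cumulative dose.** A simulation was run with an assumed hazard that rises with daily dose (HR 2 per unit), under three assumed scenarios. Time-updated cumulative dose kept the correct sign in all three (log HR 0.30 to 0.64). A total fixed at the end of follow-up reversed it (−1.3 to −2.9). Crude rates across cumulative-dose bands rose under a constant hazard (0.019 to 0.025), but fell with an early hazard peak (0.082 to 0.024) or depletion of susceptible patients (0.174 to 0.116). The protocol does not say which construction will be used.

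**Precision of an unconditional exposure-by-dose term.** Assume half the users are at a higher dose. The ratio of hazard ratios detectable with 80% power is exp[2.8016 × 2 / √(0.1418 D)]: 1.97 (484 events), 2.24 (339), 2.53 (258) and 3.02 (181).

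**The case against.** The main evidence is the Cox hazard ratio for concomitant use against digoxin or statin alone. In Section 2, dose-related describes the adverse events of the co-administered drug, not a gradient that must be shown. Dose-response is called further analysis, and making a secondary analysis conditional is a legitimate choice. This stands: a reader might infer that dose-response is the core evidence, and the documents do not support that.

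A reader might also infer that the dose analysis will point the wrong way, because patients who tolerate the combination longest accumulate the highest totals. The text does not support that either. The result depends on how cumulative dose is built and on the time course of risk, both unstated; the construction may properly sit in an analysis plan. Reversal is a risk, not a consequence of the wording.

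Dose is not ignored when the condition fails, since daily dose is adjusted for in every model and the statin analysis at equivalent doses may run anyway. Section 3.3 also names no cumulative metric, so it does not exclude a daily-dose check. These points soften the concern, but none of them guarantees an exposure-by-dose estimate.

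Finally, frequent skipping depends on the effect assumed. If 30% of users at a high dose had HR 2 and the rest HR 1 (both assumed), with equal baseline risk, the pooled value would be 0.7 × 1 + 0.3 × 2 = 1.3. If baseline risk at high dose were double, it would be (0.7 + 0.3 × 2 × 2) / (0.7 + 0.3 × 2) = 1.46, and the skip rates would fall to about 12-25% (digoxin) and 37-52% (statins). Dilution is therefore weaker when baseline risk rises with dose.

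**Conclusion.** The concern holds in a limited form. As written, the plan can report a null pooled result with no estimate of whether the dronedarone effect varies with dose. Its trigger wording is inconsistent, and its named metrics do not match its own dose variable.

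The condition is a substantial obstacle at true pooled hazard ratios around 1.3. A reader might infer that the analysis will usually be skipped; at the design hazard ratios the plan's own power makes the nominal rate 20%, so that general claim is not supported.

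The figures rest on Schoenfeld's approximation, a two-group comparison, 17.1% exposure as predicted by the sponsor, and events derived from cohort size and baseline rate. The high-dose shares and the simulated hazards are assumptions, not figures from the protocol. This is a worthwhile, inexpensive improvement and does not undermine the main analysis.

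**What to change.** - In the synopsis (exposure and statistical paragraphs) and in Sections 3.3 and 3.7, delete the condition. This also settles the conflict between the two triggers.
- State that, for each outcome, the dronedarone hazard ratio will always be reported by average or current daily dose of digoxin, or of statin in the equivalent units already listed in Section 3.3. Fit it as an exposure-by-dose term with confidence intervals and label it as estimation, not as a powered test.
- Keep cumulative dose and treatment duration as supplementary, and state that cumulative dose is time-updated.
- Say that the secondary statin analysis at equally effective doses does not depend on the pooled result.

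The cost is wording plus one more model per outcome on data already held; cohort size and alpha do not change. The drawback is imprecision: with half of users at a higher dose, only ratios of hazard ratios of about 2.0-2.2 (digoxin) and 2.5-3.0 (statins) would be detectable, so a wide interval must not be read as evidence of no dose effect.
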